3.0 Scientific Endpoints*

2.1 Describe the scientific endpoint(s), the main result or occurrence under study.

*NOTE: Scientific endpoints are outcomes defined before the study begins to determine whether the objectives of the study have been met and to draw conclusions from the data. Include primary and secondary endpoints. Some example endpoints are: reduction of symptoms, improvement in quality of life, or survival. Your response should **not** be a date.*

Response:

Primary Objective

Evaluate the safety of the intervention through 42 days of follow-up as compared to the control arm as assessed by:

- Cumulative incidence of serious adverse events (SAEs)
- Cumulative incidence of Grade 3 and 4 adverse events (AEs).

- Adverse Events of Special Interest
- Discontinuation or temporary suspension of the investigational medication (for any reason).

Secondary Objectives

Evaluate the clinical efficacy of melatonin as compared to placebo as assessed by:

Hospitalization: Incidence of COVID related hospitalization at 42 days.

Data will be obtained from electronic medical record.

COVID related symptoms: Fever, chills, cough, nasal symptoms, body aches/muscle aches, headache, loss of smell, loss of taste, nausea, vomiting, diarrhea, fatigue, dizziness. The speed of resolution of COVID related symptoms. Change from baseline, Day 1 to Day 42. Accessed by questionnarre.

Change in the WHO Clinical Progression Scale (0-10). Data will be obtained from electronic medical record.

Mortality: 42-day mortality. Data will be obtained from electronic medical record.

Exploratory Objective

Evaluate the effect of melatonin on virologic parameters as compared to placebo and assessed by:

-Percent of subjects with SARS-CoV-2 detectable in saliva sample at days 1, 3, 7, 14, 28 and 42.

-Quantitative RT-PCR for SARS-CoV-2 virus in saliva sample at days 1, 3, 7, 14, 28 and 42.

-Evaluate the reduction in cytokine/chemokine RNA and/or protein levels in saliva:

-Reduction as compared to baseline (Day 1) in salivary levels of cytokine/chemokine RNA and/or protein (IL-1, IL-2, IL-3, IL-4, IL-6, IL-8, IL-10, IL-11, IL-12, IL-13, IL-17, IL-18, TNF α , IFNy, IFN α , IFN-B, MCP1) at days 3, 7, 14, and 28.

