12.0 Procedures Involved*

12.1 Provide a description of *all research procedures or activities* being performed and when they are performed once a subject is screened and determined to be eligible. Provide as much detail as possible.

NOTE: This should serve as a blueprint for your study and include enough detail so that another investigator could pick up your protocol and replicate the research. For studies that have multiple or complex visits or procedures, consider the addition of a schedule of events table in in your response.

Response: Because of the highly contagious nature of COVID infection in the first few days after onset of symptoms, it is essential to minimize exposure of research team members to the subjects. Therefore, except for the enrollment visit, all procedures for this study will be conducted remotely at the subject's home. The Table below depicts all the research procedures.

	Screen	Enrollment							
Day +/- Window	-1 or 1	1	Daily until	Daily until	Day 3 ± 1	Day 7 ± 1	Day 14 ± 2	Day 28 ± 3	Day 42 ± 3

			day 14	day 42					
Assessments/Procedures									
ELIGIBILITY									
Informed consent	X								
Demographics & Medical History	X								
Prior SARS-CoV-2 based on screening or perform rapid antigen testing	X								
STUDY INTERVENTION									
Randomization		X							
Administration of Melatonin/Placebo		X	X						
STUDY PROCEDURES									
Body temperature		X	X	X	X	X	X	X	X
Clinical data collection		X	X	X	X	X	X	X	X
Pulse Oximetry measurement		X	X	X	X	X	X	X	X
Adverse event evaluation		X			X	X	X	X	X
RESEARCH LABORATORY									
Saliva for PCR SARS-CoV-2		X			X	X	X	X	X
Saliva for Cytokine/Chemokine RNA and/or protein		X			X	X	X	X	X

Below is a day by day description of the study procedures.

- For those subjects that have not had a COVID-test: Subjects will be enrolled and then tested for SARS-CoV2 using an EUA rapid antigen administered by the study team. If negative by rapid antigen test subjects will be withdrawn from study. Those subjects that have a prior positive test will not be give a rapid antigen test.
- If COVID-19 positive:
- Collect a baseline sample of saliva prior to taking drug, by spitting in a collection container that will be provided at time of consent.
- Rate COVID symptoms before starting medication and then each day in the evening on a short questionnaire from Day 1 to Day 42.
- Record body temperature and pulse oximetry each day in the morning and evening.

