Statistical analyses: Analyses will be performed with a focus on estimation of specific clinically important parameters, including preliminary evidence of safety and activity of the intervention, for use in the planning of subsequent comparative trials designed to fully assess safety and efficacy. The primary outcomes in the examination of the study intervention, specifically, the cumulative incidence of serious adverse events (SAEs), the cumulative incidence of Grade 3 and 4 adverse events (AEs), and the discontinuation or temporary suspension of the investigational medication (for any reason), are measured in a binary fashion at the

study participant-level. The corresponding probabilities will each be estimated using the relative frequency. In addition to the point estimates based on collected data, 95% confidence intervals will also be computed based on the methodology of Clopper and Pearson. Additional binary study outcomes, ex., incidence of COVID-related hospitalization and hospitalization for any reason, will be analyzed in an identical fashion. Comparison between randomized groups with regards to these outcomes will be done using Fisher's exact test. For numeric outcomes, such as symptom questionnaire results and measures of clinical improvement, the rank-based Wilcoxon rank sum test will be used to compare groups. For outcomes which may be subject to censoring such as speed of resolution of COVID related symptoms, parameter estimation will be based on the Kaplan-Meier estimator and the log-rank test will be utilized to compare groups. Proposed exploratory outcomes are collected longitudinally. Proposed exploratory outcomes are collected longitudinally. Standard statistical techniques for the analysis of such outcomes, ex., mixed linear models, will be utilized. Although primary analyses will be performed based on the intent-to-treat principle, to evaluate the robustness of these results, analyses will also be conducted in a secondary fashion based on actual treatment received. All statistical tests will be two-sided and tested at a 0.05 nominal significance level. All analyses will be carried out using SAS version 9.4 (or higher) statistical software (Cary, NC).

19.2 *If applicable, provide a power analysis.*

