21.0 Provisions to Monitor the Data to Ensure the Safety of Subjects*

N/A: This study is not enrolling subjects, or is limited to records review procedures only. This section does not apply.

NOTE: Minimal risk studies may be required to monitor subject safety if the research procedures include procedures that present unique risks to subjects that require monitoring. Some examples include: exercising to exertion, or instruments that elicit suicidality or substance abuse behavior. In such cases, N/A is not an acceptable response.

21.1 Describe the plan to periodically evaluate the data collected regarding both harms and benefits to determine whether subjects remain safe.

Response: On a weekly basis the co-PIs will review the data being collected to determine if there are any worrisome patterns of the adverse events (grade 3 or 4) and SAEs reported. This review will be blinded. We do anticipate a 20% rate of hospitalization in our subjects. Therefore, only if the rate is much higher than that will there be a cause of concern.

21.2 Describe what data are reviewed, including safety data, untoward events, and efficacy data.

Response: All safety data will be reviewed.

External Review of Data

[name], an infectious disease specialist at University of Buffalo will serve as an external reviewer for the outcomes collected in this study. Specifically, he will adjudicate whether the adverse events (grade 3 or 4) and SAEs collected are drug or disease related. He will also adjudicate whether the hospitalizations observed in this study were COVID related or not. These adjudications will be on blinded data.

21.3 Describe any safety endpoints.

- Response: Cumulative incidence of serious adverse events (SAEs)
 - Cumulative incidence of Grade 3 and 4 adverse events (AEs).
 - Adverse effects of special interest: Anxiety and Depression (GAD-2 and PHQ-2 questionnaires); Drowsiness (will be recorded)
 - Discontinuation or temporary suspension of the investigational medication (for any reason).

21.4 Describe how the safety information will be collected (e.g., with case report forms, at study visits, by telephone calls with participants).

Response: The safety information will be collected by scheduled phone calls as described above.

21.5 Describe the frequency of safety data collection.

Response: Days 1, 3, 7, 14, 28 and 42

21.6 Describe who will review the safety data.

Response: The co-PIs will review the data along with the biostatistician [name].

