23.0 Risks to Subjects*

23.1 List the reasonably foreseeable risks, discomforts, hazards, or inconveniences to the subjects related to their participation in the research. Consider physical, psychological, social, legal, and economic risks. Include a description of the probability, magnitude, duration, and reversibility of the risks.

NOTE: Breach of confidentiality is always a risk for identifiable subject data.

Response:

Nasopharyngeal swabs are associated with discomfort that is usually short-lived.

Potential risks associated with the use of planned doses of melatonin include dizziness, headache, vivid dreams, nausea and sleepiness, that are anticipated to be of mild severity.

Breach of confidentiality is an associated risk of this research.

23.2 Describe procedures performed to lessen the probability or magnitude of risks, including procedures being performed to monitor subjects for safety.

Response: The frequent telephonic follow-up and the availability of the study team to the participants in case adverse effects arise.

Please see section 20.1 for procedures performed to lessen the risk of breach of confidentiality.

23.3 If applicable, indicate which procedures may have risks to the subjects that are currently unforeseeable.

Response: Melatonin has never been studied in COVID patients, therefore there are unforeseeable risks.

23.4 If applicable, indicate which research procedures may have risks to an embryo or fetus should the subject be or become pregnant.

Response: Melatonin has not been studied in pregnancy.

23.5 If applicable, describe risks to others who are not subjects.

Response: NA

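### Symptom scores are compared by an unadjusted Wilcoxon test, with the tested score and day left open; rank-based ANCOVA on the Day 1 score would usually be more precise at almost no cost

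*Combined protocol and SAP*

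**What the plan says.** Section 19.1 assigns tests by type of outcome. Its rule for numeric variables reads: "such as symptom questionnaire results and measures of clinical improvement, the rank-based Wilcoxon rank sum test will be used to compare groups". Where an outcome can be censored, as with speed of symptom resolution, "parameter estimation will be based on the Kaplan-Meier estimator and the log-rank test will be utilized to compare groups". Mixed models are kept for the exploratory outcomes. Baseline variables appear in the analysis plan only for descriptive summaries.

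The Day 1 score is collected. Section 12.1 lists the step "Rate COVID symptoms before starting medication and then each day in the evening on a short questionnaire from Day 1 to Day 42".

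Section 3.0 describes the symptom endpoint as "The speed of resolution of COVID related symptoms. Change from baseline, Day 1 to Day 42". Neither this entry nor Section 19.1 says which quantity goes into the Wilcoxon test (the follow-up score or the change), or on which of the rating days.

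On purpose, Section 19.1 states that "Analyses will be performed with a focus on estimation of specific clinically important parameters", including early evidence of safety and activity, "for use in the planning of subsequent comparative trials designed to fully assess safety and efficacy".

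**The concern.** A symptom score taken before treatment often predicts the score later in the illness. The planned test either ignores the Day 1 score (if the follow-up score is ranked) or uses it only by subtraction (if the change is ranked). Both can be noisier than adjusting for it.

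Subtraction has a particular weakness here. The subjects are outpatients with mild or moderate disease followed to Day 42, and many may be symptom-free by then. For anyone whose follow-up score is zero, the change equals minus the Day 1 score and holds no further information on treatment.

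At stake is the precision of one secondary comparison between 20 and 10 subjects, in a pilot meant to inform later trials. The primary safety objective is not affected.

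**Working it through.** **Inputs from the protocol.** N = 30 (Sections 1.0 and 7.1), allocated 2:1 (Section 19.1), with 20 on melatonin (Section 19.2) and so 10 on placebo; tests two-sided at 0.05 (Section 19.1).

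**The plan's own precision figure.** Section 19.2 bounds the standard error of a safety proportion at 11 percentage points. sqrt(0.5 × 0.5 / 20) = 0.1118, which agrees after rounding. No precision or power is stated for symptom scores.

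**Assumed, because the documents give no values.** Correlation r between Day 1 and follow-up scores of 0 to 0.7; equal variance on both days; a 1 SD treatment effect; various shares of placebo subjects at zero.

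**Linear-model variances, relative to the follow-up score.**
- Follow-up (raw) score: 1
- Change score: 2(1 − r)
- ANCOVA: (1 − r²) × (n − 3)/(n − 4) = (1 − r²) × 27/26. The last factor is the average small-sample cost of one covariate.

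| r | ANCOVA / raw | ANCOVA / change | N for equal precision, raw | N for equal precision, change |
|---|---|---|---|---|
| 0.3 | 1.038 × 0.91 = 0.945 | 0.945 / 1.4 = 0.675 | 30 / 0.945 = 32 | 30 / 0.675 = 44 |
| 0.5 | 1.038 × 0.75 = 0.779 | 0.779 / 1.0 = 0.779 | 30 / 0.779 = 39 | 30 / 0.779 = 39 |
| 0.7 | 1.038 × 0.51 = 0.530 | 0.530 / 0.6 = 0.883 | 30 / 0.530 = 57 | 30 / 0.883 = 34 |

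Break-even against the raw score: (27/26)(1 − r²) = 1, so r = sqrt(1/27) = 0.19. At r = 0 the ratio is 27/26 = 1.04, a 4% larger variance.

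**Check on ranks.** Simulated power at 20 vs 10 with integer scores floored at zero and permutation p-values (4,000 runs, 999 permutations each):

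| Placebo recovered | r | Wilcoxon, follow-up | Wilcoxon, change | Rank ANCOVA |
|---|---|---|---|---|
| no floor | 0 | 0.67 | 0.40 | 0.66 |
| no floor | 0.5 | 0.68 | 0.67 | 0.77 |
| 30% | 0.5 | 0.60 | 0.26 | 0.66 |
| 60% | 0 | 0.45 | 0.08 | 0.48 |
| 60% | 0.5 | 0.47 | 0.09 | 0.51 |
| 80% | 0.5 | 0.17-0.18 | 0.05 | 0.34 |

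A separate simulation with 50% of placebo at zero and r from 0.3 to 0.7 gave about 0.14-0.18 for the change, 0.52-0.54 for the follow-up score and 0.54-0.64 for rank ANCOVA. Rank ANCOVA had more power than Wilcoxon on the change in every setting tried. Its type I error in the permutation runs was 0.040 to 0.057.

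On the rank scale, the variance of the adjusted difference in mean ranks relative to the unadjusted one was 0.96-0.99 at r = 0.3, 0.81-0.93 at 0.5 and 0.58-0.80 at 0.7, and 1.03-1.05 at r = 0. The upper ends belong to the settings with most zeros, so the linear ratios flatter the gain over the raw score when many scores tie.

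**Heavy ties.** With 80% of placebo at zero and normal-approximation p-values, Wilcoxon on the follow-up score appears slightly better than rank ANCOVA (about 0.35 against 0.31). With permutation p-values the order reverses (0.17-0.18 against 0.30-0.35). Much of this is discreteness: the raw permutation test then rejects only 0.024-0.032 of the time under the null. It is a reason to fix the p-value method in advance, not evidence of extra information in the Day 1 score.

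**The case against.** **The comparator.** A reader might infer that the plan tests the change from baseline and so stands to lose most of its power. The documents do not establish this. In Section 3.0 the phrase on change follows directly on speed of resolution, which Section 19.1 sends to Kaplan-Meier and log-rank; it may only describe the observation window. Section 19.1 speaks of questionnaire results and mentions no change. The large contrasts are therefore conditional. What stands without that reading is the missing specification and the smaller gain over the raw score.

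**Is the gain free?** No. Below r of about 0.19 there is none over the raw score, and at r = 0 there is a small loss.

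**Does it serve estimation?** Only in part. Rank ANCOVA mainly gives a p-value and an adjusted difference in mean ranks, not an effect in clinical units. A proportional-odds model with the same covariate could supply an odds ratio, but its likelihood-ratio test had type I error of 0.058-0.085 in simulation at this size, so it should not be the test.

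**Symptom overlap.** Section 23.1 says that the risks of "melatonin include dizziness, headache, vivid dreams, nausea and sleepiness, that are anticipated to be of mild severity", and dizziness, headache and nausea are also endpoint symptoms. A reader might infer that the symptom comparison is biased. It is not: the randomised comparison validly estimates the net effect of treatment on symptoms. An analysis without those three symptoms is optional.

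**Conclusion.** The point holds as a cheap improvement. The planned test is valid; what can be lost is precision, on a secondary endpoint. The protocol leaves the tested score and day open and makes no use of the Day 1 score as a covariate.

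Against the follow-up score, the linear-model variance reduction is about 5%, 22% and 47% at r = 0.3, 0.5 and 0.7, and less on ranks when many scores are zero. Against the change score it is about 32%, 22% and 12%, and the power gap becomes large once many subjects have recovered. The size rests on assumed correlations, effect and recovery shares. The direction against the change score was the same in every setting examined; against the raw score it depends on r exceeding about 0.19.

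**What to change.** In Section 19.1, replace the Wilcoxon test for symptom scores with wording such as: *The symptom questionnaire score at Day [one named day] will be compared between groups by rank-based ANCOVA with the pre-dose Day 1 score as covariate. P-values will come from permuting treatment labels in line with the randomisation scheme, because many scores may tie at zero. The change score will not be tested.*

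Keep Kaplan-Meier and log-rank for speed of resolution. A Cox model adjusted for the Day 1 score is optional: in simulation it did not shrink the standard error of the log hazard ratio (0.445 to 0.468 in one setting, 0.435 to 0.465 in another), and any gain in power came from a larger conditional effect.

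The cost is one degree of freedom, a few lines of text and a short permutation routine, with no extra visits, subjects or data. If the Day 1 score carries no information, the variance is about 4% larger. Since the plan does not impute, a subject without a Day 1 score would drop out of the adjusted comparison.

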19.0 Data Management and Analysis*

19.1 *Describe the data analysis plan, including any statistical procedures. This section applies to both quantitative and qualitative analysis.*

Response:

Randomization: Participants will be randomized to the intervention or control arm in a 2:1 fashion using a permuted block randomization scheme. The randomization lists to be used in this study will be generated by the study biostatistician. Subjects will be included in data analyses according to their randomized assignment irrespective of the treatment actually received (intent-to-treat).

Missing data: The amount and nature of missing data will be characterized and no method of imputation will be used for missing data. We acknowledge the possibility of informative missingness with some of the outcomes, that is, the probability of a particular observation being missing may be related to the health or death of a subject, and therefore analyses will be interpreted with caution.

Accrual: Participants will be accrued to the study on a first-come basis. The projected accrual is approximately 15 per month, and therefore recruitment is expected to be complete at most 60 days following the study starting point. Subjects will be followed for 1 month after recruitment completion, so total study duration will be approximately 3 months. During the enrollment period, the study biostatistician will model and predict accrual rates in order to verify adequacy of the enrollment process.

Descriptive analyses: Measured outcome variables will be summarized overall and by relevant demographic and baseline variables. Descriptive statistics such as frequencies and relative frequencies will be computed for all categorical variables. Numeric variables will be summarized using simple descriptive statistics such as the mean, standard deviation and range. A variety of graphical techniques will also be used to display data, ex., histograms, boxplots, scatterplots, etc.

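### Section 19.1 has no rule for hospitalization or death in the symptom-resolution analysis, so with no imputation the sickest subjects are likely to be censored or left out as if uninformative

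*Combined protocol and SAP*

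**What the plan says.** Section 3.0 lists as a secondary endpoint "The speed of resolution of COVID related symptoms. Change from baseline, Day 1 to Day 42". It does not say what counts as resolved. Hospitalization, the WHO scale and 42-day mortality are separate secondary outcomes taken from the medical record.

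Section 12.1 gives the source of the symptom data: "Rate COVID symptoms before starting medication and then each day in the evening on a short questionnaire from Day 1 to Day 42". It also says that "except for the enrollment visit, all procedures for this study will be conducted remotely at the subject's home". Under section 14.1 the questionnaire is handed over at consent and collected from the home by courier. No section provides for rating symptoms in hospital.

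Section 19.1 sets three rules that meet on this endpoint:

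- Kaplan-Meier and log-rank are used "For outcomes which may be subject to censoring such as speed of resolution of COVID related symptoms".
- Numeric symptom questionnaire results are compared by the Wilcoxon rank sum test.
- For gaps, "no method of imputation will be used for missing data". The same paragraph concedes that "the probability of a particular observation being missing may be related to the health or death of a subject", and answers this only with a promise of cautious interpretation.

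Section 21.1 states: "We do anticipate a 20% rate of hospitalization in our subjects". Nowhere does the plan say when a subject is censored, or how an admission or a death enters the symptom analyses.

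**The concern.** Kaplan-Meier and log-rank assume that censored subjects would have gone on to resolve at the same rate as those still observed. A subject who dies does not go on to resolve, and a subject sick enough to be admitted is unlikely to resolve at the pace of those at home. If the time is cut at death or at the last diary entry, the sickest subjects leave the risk set and the resolution curve of those who remain stands in for them. The Wilcoxon test has a parallel problem: a subject without a score on the day compared has no rank and falls out, which also sits badly with the intent-to-treat principle in 19.1.

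Two things are at stake. The level of resolution is overstated in both arms, and section 19.1 wants these estimates for planning later trials. If admission rates differ between arms, the arm with more admissions loses more of its poor outcomes from the symptom comparison, so a real difference in either direction shrinks. And because no rule is written down, it could be chosen after the data are seen.

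**Working it through.** **The plan's own figures.** The only precision figure, in 19.2, is for the safety probabilities: sqrt(0.5 × 0.5 / 20) = 0.112, against a stated maximum of 11 points. It agrees after rounding and does not bear on this endpoint. There is no power or event figure for symptom resolution to reproduce. The anticipated number of admissions is 0.20 × 30 = 6: 4 of 20 on melatonin and 2 of 10 on placebo if rates are equal under the 2:1 allocation.

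**Simplest case.** Suppose 4 of 20 subjects in one arm are admitted early and the other 16 resolve by Day 42. Kaplan-Meier with the 4 censored at admission ends at 100% resolved. Counting the 4 as not resolved gives 16/20 = 80%.

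**Illustration with unequal rates.** These assumptions are not in the documents:

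- Resolution is exponential with median 10 days in subjects not admitted, the same in both arms.
- A fraction h is admitted on Day 6: 15% on melatonin, 30% on placebo. The pooled rate is (20 × 0.15 + 10 × 0.30)/30 = 20%, matching section 21.1.
- No admitted subject has resolved by Day 14.

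True proportion resolved by Day 14 = (1 − h)(1 − 2^−1.4) = (1 − h) × 0.621:

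- Melatonin: 0.85 × 0.621 = 52.8%
- Placebo: 0.70 × 0.621 = 43.5%
- Difference: 9.3 points

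Kaplan-Meier with permanent censoring at admission. Unresolved on Day 6 is h + (1 − h) × 2^−0.6. From Day 6 to Day 14 only non-admitted subjects remain at risk, with conditional probability 2^−0.8 = 0.574 of staying unresolved:

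- Melatonin: 1 − (0.15 + 0.85 × 0.660) × 0.574 = 1 − 0.711 × 0.574 = 59.2%
- Placebo: 1 − (0.30 + 0.70 × 0.660) × 0.574 = 1 − 0.762 × 0.574 = 56.2%
- Difference: 2.9 points

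So (9.3 − 2.9)/9.3, about 69% of the difference, is lost, and the arms look better than they are by about 6 and 13 points.

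**Range over the unknown rule.** Let a share f of admitted subjects be permanently censored and the rest stay at risk as unresolved. After Day 6 the conditional probability of staying unresolved becomes [(1 − h) × 0.379 + (1 − f)h] / [(1 − h) × 0.660 + (1 − f)h], with 0.379 = 2^−1.4.

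| Share censored, f | Melatonin | Placebo | Difference |
|---|---|---|---|
| 0 (all kept at risk) | 52.8% | 43.5% | 9.3 points |
| 0.5 | 55.6% | 48.3% | 7.3 points |
| 1 (all censored) | 59.2% | 56.2% | 2.9 points |

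**Equal rates.** With h = 20% in both arms the truth is 0.80 × 0.621 = 49.7%, and Kaplan-Meier with censoring gives 1 − (0.20 + 0.80 × 0.660) × 0.574 = 58.2%. Each arm is overstated by 8.5 points and the contrast is unaffected.

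**Second check, by simulation with other assumptions.** Admission fell on Days 3 to 10, only in unresolved subjects, with the same 10-day median. The comparator counted admitted subjects as unresolved through Day 42, a stronger assumption than above. With realised admission of 26% on melatonin v 6% on placebo, Day-42 resolution was 94.5% in both arms with censoring, against 71% v 89% with admitted subjects counted as unresolved. The mean log-rank z for 20 v 10 subjects moved from −0.06 to −0.91. With equal realised rates (13% v 13%), both arms moved from about 95% to 83% and z hardly changed.

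**The case against.** A reader might infer that the plan censors subjects at admission. It does not say so. Section 19.1 notes only that the outcome may be censored; keeping an admitted subject at risk as unresolved also fits the text, and then the illustration shows no bias. Admission need not end the diary either: it runs to Day 42 and can resume after discharge, section 12.1 has telemedicine contacts on Days 3, 7, 14, 28 and 42, section 8.1 requires an emergency contact, and section 12.4 gives remote access to medical records. Only death certainly ends self-rating. All this stands, and it is why the effect of admission is put as probable and the figures as one hypothetical. It does not supply a rule, and periodic contacts do not replace a daily rating.

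A reader might also infer that harm would be hidden in the trial as a whole. The documents do not support that. SAEs are a primary outcome, and hospitalization is estimated by arm and compared by Fisher's exact test. Mortality and the WHO scale come from the medical record. An excess of admissions would be reported directly, but none of this repairs the symptom endpoint.

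The practical effect on testing is limited. The standard error of a difference in proportions at 0.5 is sqrt(0.25/20 + 0.25/10) = 19 points, well above the 6.4 points lost in the illustration, and the mean log-rank z stayed below 1 in size under either rule. That lowers the priority. It does not excuse a systematic error in estimates meant for planning.

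Finally, worst ranks assign values to missing scores, which conflicts with the no-imputation rule. That is right, so the exception has to be written down.

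**Conclusion.** The point holds as a gap with a predictable direction of bias, in a secondary endpoint of a pilot trial; it should be fixed but does not touch the primary safety outcomes. Home self-rating, no imputation, and Kaplan-Meier, log-rank and Wilcoxon without a rule for admission or death together make it likely that the sickest subjects are treated as uninformative. This is close to certain for death and probable for a diary that stops at admission.

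Up to about 6 of 30 subjects are affected. That is an upper bound, since it includes anyone admitted after resolving and anyone who resumes the diary. The level of resolution is overstated in both arms. Bias between arms needs unequal admission rates: under 15% v 30% with Day 6 admission, none of those admitted resolved by Day 14 and permanent censoring, 9.3 points shrink to about 3; with all kept at risk, nothing is lost. The documents give no resolution rate, admission day or split by arm, so these sizes are illustrative.

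**What to change.** In section 19.1:

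- Define resolution, and state that a hospitalized subject stays at risk as unresolved until later ratings show resolution.
- Count death as never resolved: censor at Day 42, not at the date of death. Treating death as a competing event with a cumulative incidence estimate is equivalent when there is no other loss before Day 42.
- As a stated exception to the no-imputation rule, give subjects who are dead or in hospital on the day of comparison the worst ranks in the Wilcoxon test, with death worst, and name that day.
- Take admission, discharge and death dates from the medical record. That these dates can be had is an inference from sections 3.0 and 12.4; the data collection forms are attachments not available here, so confirm that they capture them.

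The cost is a few lines of text and minor programming, with no added visits or subjects. The downside is that resolution looks slower in both arms and the symptom endpoint becomes partly a composite with serious outcomes.
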